#### 1.0 STUDY SUMMARY

Name of Sponsor:	Compound:
Takeda Pharmaceutical Company Limited	TAK-906
Study Identifier: TAK-906-1004	Phase: 1

**Protocol Title:** A Randomized, Double-Blind, Placebo-Controlled, Single and Multiple Ascending Dose, Phase 1 Study to Evaluate the Safety, Tolerability, Pharmacokinetics, and Pharmacodynamics of TAK-906 in Japanese Healthy Male Subjects

#### **Trial Design:**

This is a phase 1, randomized, double-blind, placebo-controlled, single and multiple ascending dose, parallel-group study in up to 3 cohorts of Japanese healthy male subjects, to assess the safety, tolerability, pharmacokinetics (PK) and pharmacodynamics (PD) of TAK-906.

Each cohort will consist of 8 subjects where 6 subjects will be randomized to receive TAK-906 and 2 subjects will be randomized to receive matching placebo. The study population will be 24 Japanese healthy male subjects. The randomized subjects will receive a single dose of blinded study drug on Day 1 followed by multiple doses of blinded study drug twice daily (BID) for 5 days from Day 3 to Day 7, except that an evening dose of study drug will not be administered on Day 7. If a subject discontinues from the trial, a replacement subject may be enrolled, if deemed appropriate by the investigator and Sponsor. The investigational site should contact the Sponsor for the replacement subject's medication identification number.

In Cohorts 1 and 2, subjects will be randomized to receive TAK-906 maleate 50 mg, 100 mg, or matching placebo. In Cohort 3, subjects will be randomized to receive TAK-906 maleate 10 mg, or matching placebo. For each cohort, follow-up assessments will occur on Day 14 which is 7 days after completion of the last treatment dose. Dose escalation to Cohort 2 will be based on a full blinded review of safety and tolerability data until follow-up assessments from Cohort 1. Cohort 3 will be conducted in parallel with Cohort 1 or 2. Dose level in Cohort 2 may be changed within the range up to 100 mg, as appropriate, based on safety and pharmacokinetic data in preceding cohorts, ie, 50 mg BID in Cohort 1 or 10 mg BID in Cohort 3 (if applicable) of this study; however, no higher dose than the proposed highest dose (100 mg BID) based on the exposures from the previous study **CCL** will be given without Sponsor and institutional review board (IRB) approval to revise the study protocol.

In either Cohort 1, 2, or 3, each subject will be confined from Day -1 to the morning of Day 8 and discharged after the investigator's confirmation of no significant abnormality in his health through physical examination and tests on Day 8, at 24-hour after the morning dose of Day 7.

A single dose and all morning doses of trial medication in multiple dose periods will be administered orally after fast of at least 10 hours that continues for at least 4 hours after dosing with restriction of water intake for at least 1 hour prior to and after dosing. The evening dose will be administered 12 hours after the morning dose and at least 2 hours after dinner. On Day 7, the trial medication will be administered only in the morning.

The study drugs include TAK-906 maleate and matching placebo capsules. The capsules all have the same appearance.

#### **Trial Primary Objective:**

To evaluate safety and tolerability of single and multiple oral doses of TAK-906 in Japanese healthy male subjects.

#### **Trial Secondary Objectives:**

To evaluate PK and PD of single and multiple oral doses of TAK-906 in Japanese healthy male subjects.

Trial Subject Population: Japanese healthy adult male subjects aged 20 to 60 years, inclusive.

Planned Number of Subjects:	Planned Number of Sites:
Per cohort: 8 each (Cohorts 1, 2, and 3)	Estimated total: 1 site
(TAK-906: 6, placebo: 2)	
Estimated total: 24 (treated)	

Dose Levels:	Route of Administration:
Single dose period: 10, 50, or 100 mg TAK-906 maleate single dose or placebo.	Oral
Multiple dose period: 10, 50, or 100 mg TAK-906 maleate BID or placebo.	
Duration of Treatment:	Planned Trial Duration:
Single dosing on Day 1 and BID dosing for 5 days on	Screening period: Days -28 to -2
Days 3 to 7 (morning dose only on Day 7), for a total of	Check-in: Day -1
6 dosing days.	Treatment period: Days 1 to 8
	(single dose period: Days 1 and 2, multiple dose period: Days 3 to 8)
	Follow-up period: Days 9 to 14

#### Main Criteria for Inclusion:

- The subject is a Japanese healthy adult male, aged 20 to 60 years, inclusive, at the time of informed consent.
- The subject weighs at least 50 kg and has a body mass index (BMI) from 18.5 to 25 kg/m^2, inclusive at Screening.
- A male subject who is nonsterilized and sexually active with a female partner of childbearing potential agrees to use adequate contraception from the signing of informed consent to 12 weeks (84 days) after the last dose of study drug. The female partner of a male subject should also be advised to use adequate contraception.

#### Main Criteria for Exclusion:

- The subject has a history of any psychiatric disease that would interfere with the evaluation of study drug activity (prolactin concentration) or safety.
- The subject has a history of seizure or tardive dyskinesia.
- The subject has a history of hyperprolactinemia, pituitary adenoma, and/or hypothyroidism.
- The subject has a family history of prolonged QT.
- The subject has undergone previous gastric bypass surgery or currently has a gastric band fitted.
- The subject has dysphagia and/or inability to swallow study medication whole.
- The subject has a QT interval by the Fridericia correction method (QTcF) of >450 msec on the electrocardiogram (ECG) at Screening, at Check-in (Day -1), or prior to the first dose of study drug (Day 1 predose).
- The subject has abnormal Screening or Day -1 laboratory values that suggest a clinically significant underlying disease or any subject with the following lab abnormalities:
  - Transaminase (alanine aminotransferase and/or aspartate aminotransferase) and/or total bilirubin >1.5  $\times$  upper limit of normal.
  - Creatinine >1.2 mg/dL.

#### Main Criteria for Evaluation and Analyses:

The primary endpoint of the study:

• Safety and tolerability will be assessed through treatment-emergent adverse events (TEAEs) including corrected QT interval prolongation associated AE, neurologic AE, and hyperprolactinemia associated AE, physical examinations, vital signs, clinical laboratory tests, and 12-lead electrocardiogram (ECG).

The secondary endpoints will be assessed through evaluation of the following parameters:

- PK: Plasma and urine concentrations of TAK-906 and its metabolite M23.
- PD: Serum prolactin level.

#### **Statistical Considerations:**

#### Safety:

The following analyses will be based on the Safety Analysis Set.

A treatment-emergent AE (TEAE) is defined as an AE whose date of onset occurs on or after the start of study drug. TEAEs will be coded using Medical Dictionary for Regulatory Activities (MedDRA) dictionary. Frequency distribution will be provided by system organ class and preferred term for each regimen. TEAEs will be summarized by pooled placebo and each TAK-906 dose level for single dose period and combined single and multiple dose periods.

For continuous variables, the observed values and their changes from baseline will be summarized by dose over each scheduled sampling time using descriptive statistics. For categorical variables, shift tables showing the number of subjects in each category at baseline and each post-baseline visit will be provided by dose.

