#### TAK-906 Study No. TAK-906-1004 Protocol

	Screening	Check-in	Single Do	ose Peri	iod		Mul	tiple D	Dose Po	eriod			Follow-up
Study Day:	Days -28 to -2	Day -1	Predose Day 1	Day 1	Day 2	Day 3	Day 4	Day 5	Day 6	Day 7	Day 8	Early Termination Visit	Day 14
PK Evaluations													
Plasma sample for TAK-906 PK (e)			Х	X	X	Х	Х	X	X	Х	Х	X (j)	
Urine sample for TAK-906 PK (f)			Х	X	X					X			
PD Evaluations													
Serum sample for PD (g)			X	X	X	Х	Х	X	X	Х	Х	Х	X
ĊĊĬ													
				X									
Other													
Confinement		X	Х	X	X	Х	Х	X	X	X	X	X (j)	

Footnotes are on the following page.

AE=adverse event, BMI=body mass index, CCI and the control of the

- (a) Where applicable, all assessments will be conducted in the morning (predose on dosing days) except for Screening, Check-in, and Follow-up.
- (b) Vital sign measurements will occur:

Days 1-2: Predose, 1, 2, 4, 6, and 24 hours post single dose.

Days 3-6: Before morning dose.

Days 7-8: Predose, 1, 2, 4, 6, and 24 hours post morning dose.

Day 14

(c) 12-lead ECG measurements will occur:

Days 1-2: Predose, 1, 2, 4, 6, and 24 hours post single dose.

- Day 5: Predose, 1, and 2 hours post morning dose.
- Days 7-8: Predose, 1, 2, 4, 6, and 24 hours post morning dose.
- (d) TAK-906 or matching placebo will be administered as a witnessed dose at approximately 07:00-08:00 and at approximately 19:00-20:00. Daily study drug administration in the multiple dose period should be within ±5 minutes of nominal dosing times on Day 3. On Day 7, study drug administration time should be as close to the time of Day 3 dosing as possible. An evening dose of study drug will not be administered on Day 7.
- (e) Plasma sample for TAK-906 PK and M23 will be collected:

Days 1-2: Predose, 0.5, 1, 1.5, 2, 3, 4, 6, 8, 12, 16, and 24 hours post single dose.

Days 3-6: Just before morning dose.

Days 7-8: Predose, 0.5, 1, 1.5, 2, 3, 4, 6, 8, 12, 16, and 24 hours post morning dose.

(f) Urine sample for TAK-906 PK and M23 will be collected:

Days 1-2: Predose (spot), 0-6, 6-12, and 12-24 hours post single dose.

- Day 7: 0-6 and 6-12 hours post morning dose.
- (g) Serum sample for PD will be collected:

Days 1-2: Predose, 1, 2, 4, 6, and 24 hours post single dose.

Days 3-6: Just before morning dose.

Days 7-8: Predose, 1, 2, 4, 6, and 24 hours post morning dose.

Day 14

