Currently in the US, there exists a large unmet medical need because there are no approved therapies for the chronic treatment of diabetic gastroparesis. Metoclopramide, a dopamine  $D_2$  receptor antagonist, and domperidone, a peripherally-acting dopamine  $D_2/D_3$  receptor antagonist, are prokinetic agents marketed in Japan. They are known to cause extrapyramidal symptoms (EPS) and cardiovascular side effects, respectively. The most notable toxicities of metoclopramide are a category of movement disorders known as EPS [7]. EPS are caused by blockade of dopamine  $D_2$  receptors in the dorsal striatum and thus are potential side effects of all centrally-penetrant drugs that share this mechanism of action, particularly selective dopamine  $D_2$  receptor antagonists. Of greatest concern is tardive dyskinesia, a severe and often irreversible EPS. The risk of developing tardive dyskinesia increases with dose level and duration of treatment and as such, the US package insert includes a black box warning regarding the chronic use of metoclopramide for longer than 12 weeks. Domperidone is a peripherally-acting dopamine  $D_2/D_3$  receptor antagonist

TAK-906	
Study ID TAK-906-1004	Page 14 of 71
Protocol	6 June 2017

marketed for use as an antiemetic and prokinetic agent in a number of countries worldwide including Japan, although not in the US due to its cardiovascular safety profile which includes risks for drug-induced long QT syndrome, torsades de pointes, and sudden cardiac death [8].

Nonclinical in vitro and in vivo pharmacology studies have demonstrated that TAK-906 has  $D_2/D_3$  antagonism with a potency comparable to or greater than domperidone and metoclopramide. TAK-906 does not readily penetrate the blood brain barrier (BBB) and therefore it can block dopamine  $D_2/D_3$  receptors in the area postrema outside of the BBB to reduce symptoms of gastroparesis, such as nausea and vomiting, but not block those inside of the BBB which are likely to cause EPS [9][10]. In addition, TAK-906 is a very weak inhibitor of the human ether-a-go-go related gene (hERG) channel, thus reducing the potential for fatal arrhythmias [8]. Therefore, TAK-906 is expected to exhibit comparable or greater prokinetic effects and less adverse effects compared with existing products on the market, which makes TAK-906 a promising drug for the treatment of gastroparesis.

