#### 9.2.5 12-Lead ECG

A standard 12-lead ECG will be recorded. Subjects should be resting in a recumbent position for at least 5 minutes before each ECG measurement. The investigator or sub-investigator (or a qualified observer at the investigational site) will interpret the ECG using 1 of the following categories: normal or abnormal. If an ECG is abnormal, the investigator or sub-investigator (or a qualified observer at the investigational site) will judge clinical significance of the abnormality. The time that the ECG was performed will be recorded. The following parameters will be recorded on the eCRF from the subject's ECG trace: heart rate, RR interval, PR interval, QT interval, QRS interval, and QTcF.

When 12-lead ECG measurements are scheduled at the same time as blood draws, the blood draw will take priority and 12-lead ECGs will be obtained within an acceptable time window (see Appendix C).

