## **11.3** Determination of Sample Size

A sample size of 8 subjects per cohort (6 active: 2 placebo) will be used in this study, and is considered sufficient for the evaluation of TAK-906 safety, tolerability, PK and PD following oral single and multiple doses. The sample size is not based on statistical power considerations.

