7.11.3 Vital Signs

Analysis Set:	Safety Analysis Set				
Analysis Variables:	Body Temperature (°C)				
	Systolic Blood Pressure (mmHg)				
	Diastolic Blood Pressure (mmHg)				
	Respiratory Rate (bpm)				
	Pulse (bpm)				
Visit:	Day 1: Predose, 1, 2, 4, 6, and 24 hours post single dose.				
	Days 3-6: Before morning dose.				
	Day 7: Predose, 1, 2, 4, 6, and 24 hours post morning dose				
	Day 14				
Analytical Methods:	For each variable, following summary will be provided by dose.				
	(1) Summary of Vital Signs Parameters and Change from Baseline by Visit				
	Descriptive statistics for observed values and changes from baseline (each post- Day 1:				
	Predose) will be provided for each visit				
	(2) Case Plots				
	Plots over time for each subject will be presented.				
	(3) Number and Percentage of Subjects with Markedly Abnormal Values of Vital Signs				
	Parameters				
	Overall frequency distributions of MAV after first dose will be provided. If a vital sign				
	parameter has both lower and upper MAV criteria, analysis will be performed for each.				
	Further details are given in Appendix.				

7.11.4 12-Lead ECGs

Analysis Set:	Safety Analysis Set				
Analysis Variables:	Heart Rate (bpm)				
	RR Interval (msec)				
	PR Interval (msec)				
	QT Interval (msec)				
	QTcF Interval (msec)				
	QRS Interval (msec)				
	12-Lead ECG Interpretation	["Within Normal Limits",			
		"Abnormal, Not Clinically Significant",			
		"Abnormal, Clinically Significant"]			
Visit:	Day 1: Predose, 1, 2, 4, 6, and 24 hours post single dose.				
	Day 5: Predose, 1, and 2 hours post morning dose.				
	Day 7: Predose, 1, 2, 4, 6, and	24 hours post morning dose			
Analytical Methods:	For each variable other than 12-lead ECG interpretations, summary (1), (2), and (3) will be				
	provided by dose.				
	For 12-lead ECG interpretations, summary (4) will be provided by dose.				
	(1) Summary of ECG Parameters and Change from Baseline by Visit				
	CO	NFIDENTIAL			

Descriptive statistics for observed values and changes from baseline (each post- Day 1: Predose) will be provided for each visit.

(2) Case Plots

Plots over time for each subject will be presented.

(3) Number and Percentage of Subjects with Markedly Abnormal Values of ECG Parameters

Overall frequency distributions of MAV after first dose will be provided. If an ECG parameter has both lower and upper MAV criteria, analysis will be performed for each. Further details are given in Appendix.

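### Most ECGs have a plasma sample at the same nominal time, but the visible SAP never relates QTcF to concentration; one prespecified supportive model would use data already being collected

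*Protocol*

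**What the plan says.** **Endpoint and background.** Protocol 5.3.1 and SAP 5.1 place 12-lead ECG and QTc-associated adverse events within the primary safety endpoint. Protocol 4.1 attributes "risks for drug-induced long QT syndrome, torsades de pointes, and sudden cardiac death" to domperidone and describes TAK-906 as a very weak hERG inhibitor. Sections 6.3.3.1 and 10.2.9.4 still single out QTc-associated events for closer monitoring.

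**Sampling (Protocol 3.0, footnotes).**
- ECG: "Days 1-2: Predose, 1, 2, 4, 6, and 24 hours post single dose", the same pattern on Days 7-8, and predose, 1 h and 2 h on Day 5.
- Plasma: "Days 1-2: Predose, 0.5, 1, 1.5, 2, 3, 4, 6, 8, 12, 16, and 24 hours post single dose", the same pattern on Days 7-8, and a morning trough only on Days 3 to 6.
- Protocol 9.2.5 on ECG timing: "The time that the ECG was performed will be recorded". Section 9.3 requires actual times for PK samples as well.

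**Analysis.** Protocol 11.1.5.4 gives the ECG rule in the words of the study summary: "the observed values and their changes from baseline will be summarized by dose over each scheduled sampling time using descriptive statistics". SAP 7.11.4 carries it out: "Descriptive statistics for observed values and changes from baseline (each post- Day 1" predose), by dose and visit. It adds individual plots, counts of markedly abnormal values and shift tables of the ECG interpretation. SAP 7.11.1 tabulates QTc-associated events. SAP 7.9, headed Pharmacokinetic/Pharmacodynamic Analysis, holds only separate PK and prolactin summaries. SAP 7.10 and 7.11.5 are marked not applicable.

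**The concern.** The trial collects paired QTcF and concentration over a 10-fold dose range and plans no analysis that joins them. The by-time table looks at each dose and time separately with 6 active subjects. It will show some sizeable peaks by chance, and it does not use the one feature that helps separate chance from drug effect, namely whether QTcF change rises with exposure.

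The QTcF outlier rule in SAP Appendix 1 (500 msec or more, or a rise of at least 30 msec with a value of at least 450 msec) concerns individual extremes and would rarely register a mean shift of a few msec. What is at stake is how informative this trial's QT data will be for Japanese participation in the global phase 2 study (Protocol 4.2). A model fitted only after an odd peak has been seen would also be less credible than a prespecified one.

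**Working it through.** **1. Pairing.** From Day 1 predose to Day 8 there are 6 (Days 1-2) + 3 (Day 5) + 6 (Days 7-8) = 15 nominal ECG times. Paired with plasma: 6 + 1 + 6 = 13. The Day 5 ECGs at 1 h and 2 h have no sample. Without Day 1 predose, 12 paired post-baseline times remain: 18 × 12 = 216 active pairs, or 24 × 12 = 288 with placebo at concentration 0.

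**2. No figure to reproduce.** "A sample size of 8 subjects per cohort (6 active: 2 placebo) will be used in this study", so 3 × 8 = 24 (18 active, 6 placebo). "The sample size is not based on statistical power considerations", and no QT margin, alpha or SD is given. The SD below is therefore an assumption: single-ECG within-subject SD of 6, 8 or 10 msec. A change from one baseline ECG then has SD √2 times larger: 8.49, 11.31 or 14.14 msec.

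**3. One time point, 6 active versus 6 pooled placebo.** 90% half-width = t(0.95, 10 df) × SD × √(1/6 + 1/6) = 1.812 × SD × 0.577.
- SD 6: 1.812 × 8.49 × 0.577 = 8.9 msec
- SD 8: 11.8 msec
- SD 10: 14.8 msec

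Simulation, with the SD estimated in each trial, averages 8.6, 11.5 and 14.6 msec.

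**4. Chance peaks.** Days 1-2 and 7-8 have 5 + 6 = 11 post-baseline times, so 3 × 11 = 33 dose-by-time means. With no drug effect, the largest of the 33 has a median of about 6, 8 or 10 msec. The SAP table also has three Day 5 times, making 42 means.

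**5. Concentration model.** The simulation uses a random subject effect, an active/placebo indicator, time factors and a concentration slope. Cmax is 31.2 and 71.6 ng/mL for 50 and 100 mg BID (Protocol 6.3.2). Assumed: 6.5 ng/mL for 10 mg; 40% between-subject CV; relative concentrations 1, 0.6, 0.25, 0.12 and 0.01 at 1, 2, 4, 6 and 24 h; a linear effect without delay. The 90% half-width at 71.6 ng/mL is about 5.7, 7.5 and 9.5 msec. Relative to step 3 that is 1 − 5.7/8.6 = 34% narrower at SD 6 and 1 − 9.5/14.6 = 35% narrower at SD 10.

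Cross-check: a separate calculation on all 12 paired times, with SD of change 10 msec, within-subject correlation 0.5 and multiplier 1.72, gives 7.0 msec. Rescaled to SD 6 and the normal quantile: 7.0 × (8.49/10) × (1.645/1.72) = 5.7 msec. Keeping 1.72 widens the range slightly: 5.7 × 1.72/1.645 = 6.0 and 9.5 × 1.72/1.645 = 9.9 msec.

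**6. Source of the gain (SD 6).** Simulated standard errors:
- One time point: 4.76
- Mean of the four 1 h and 2 h readings on Days 1 and 7, without concentrations: 3.83
- Concentration model: 3.41

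Share due to pooling times: (4.76 − 3.83)/(4.76 − 3.41) = 0.93/1.35 = 69%.

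**7. What stays unresolved.** With a true effect of 5 msec at Cmax, the model's 90% CI excludes zero in about 43%, 30% and 23% of trials (SD 6, 8, 10). For 3 msec the figures are about 22%, 16% and 13%.

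**The case against.** The strongest reply is that this is a descriptive, unpowered phase 1 study with no QT hypothesis, margin or exclusion claim, so leaving out an optional model contradicts nothing. That stands, and it is why the point is an improvement and not an error.

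A reader might infer that the QT assessment rests solely on noisy means of 6. The documents do not support that: plots, shift tables, outlier counts, event tables and the QTcF criteria in Protocol 6.5.4.1 and 7.6 all bear on QT. Nor do they describe TAK-906 itself as QT-prolonging; the risk is attributed to domperidone.

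Three technical objections also stand. Most of the precision gain comes from pooling times (step 6). The 6 versus 6 comparator is not itself planned, since placebo pooling is stated only for adverse events. And the ECGs appear to be single, site-read tracings with a ±30 minute window at 1 to 6 h, against ±5 minutes for plasma (Appendix C).

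The exploratory objectives are not legible in either document, so a concentration-QT aim there cannot be excluded. No such method appears in the visible SAP. Being descriptive is no bar to a model: SAP 7.9.1.2 already fits linear and power models for dose proportionality, and an estimate with an interval needs no power claim.

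**Conclusion.** The point holds as a cheap improvement. Thirteen of 15 ECG times are paired with plasma, and the visible SAP plans no concentration-QTcF analysis. A single pooled model would narrow the 90% interval at the top exposure by about a third relative to one 6 versus 6 contrast, and would show whether QTcF change follows exposure.

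The absolute widths depend on the assumed SD. The relative gain was similar across the SDs tried, but it also rests on the assumed concentration profile, linearity and absence of delay. The baseline covariate in the proposed model was not simulated.

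It would be tempting to make the model the basis for a QT conclusion, or to expect it to settle effects of a few msec. Neither follows: no formal QT conclusion is planned, the ECG timing is loose, and step 7 shows that small effects would usually remain unresolved.

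**What to change.** Keep all planned ECG outputs and add one prespecified analysis, labelled supportive and exploratory, to SAP 7.11.4:

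- **Model:** linear mixed model of change in QTcF from Day 1 predose on TAK-906 concentration, with active/placebo indicator, nominal day and time, baseline QTcF and a random subject effect.
- **Data:** all cohorts pooled; all paired post-baseline ECGs (Days 1-2, Days 7-8 and Day 5 predose). Placebo concentration is set to 0, because Protocol 9.3.1.1 leaves placebo samples unassayed.
- **Timing:** interpolate concentration to the recorded ECG time where samples bracket it. The 0.5 h and 1.5 h samples help around the 1 h ECG. State the rule for times that are not bracketed.
- **Report:** the slope, and the predicted placebo-adjusted change with 90% CI at each dose's geometric mean Cmax, with a plot to check linearity and delay.

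The cost is one SAP paragraph and one model, with no extra ECGs, samples or subjects. The text should say that the result does not replace a dedicated QT evaluation.
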